### 5.2.2. Secondary analyses

#### *Effects on secondary outcomes*

To investigate the effect of the resistance exercise intervention on the secondary outcomes (other cognitive outcomes, brain structure and function and AB), the same analyses as the primary analysis using an intention-to-treat principle and cLMM analysis will be performed. The preprocessing analysis of brain structure and function measured with MRI will be carried out as secondary analyses using different programs (Freesurfer, FSL, CON, fMRIprep).

#### *Effects on other outcomes*

To investigate the effect of the resistance exercise intervention on other outcomes (i.e., biological biomarkers, physical function, muscular strength, physical activity, Anthropometric, body composition and blood pressure and Psychosocial, mental health and other questionnaires) the same analyses as the primary analysis using an intention-to-treat principle and cLMM analysis will be performed.

Furthermore, analyses per protocol will be followed of the executive function variables (ie., Executive function score, Trail making test, Digit symbol substitution score, Dimensional change card sort test and Spatial working memory).

#### *Moderators and mediators*

In addition, mediation and moderation analysis will be performed following AGRema (A Guideline for Reporting Mediation Analyses) recommendations (46), using the group as independent variable (intervention group vs control group), executive function as outcome, and mediating and moderating variables.

Moderators include will be sex, age, education, apolipoprotein E (APOE) status, and A $\beta$  status. Additionally, baseline data of various cognitive measures, including the composite executive function score, Trail Making Test, Digit Symbol Substitution Score, Dimensional Change Card Sort Test, and Spatial Working Memory, will be incorporated. The baseline values of strength measures and mental health variables, specifically depression and self-esteem, will be also analyzed. We will also assess the potential mediators, aiming to understand the mechanisms through which the intervention could exert its effects. No interim analysis will be performed.

### 5.2.3 Sensitivity analyses

A sensitivity analysis will be performed using an intention-to-treat principle with all randomly assigned participants, but excluding participants who encountered adverse events that may have impacted the primary outcomes. Adverse events considered for exclusion is conducted to identify and categorize adverse events based on predefined criteria using common terminology criteria for adverse events (i.e., mild, moderate, severe) (47).

### 5.3 Missing data

The number of missing data will be reported and patterns of missing data will be explored. Based on previous experience, we expect that missing data will be assumed as missing at random. Therefore, the linear mixed model analyses will handle our missing data. However,

once the data processing is finalized, we reconsider this expectation. In case we believe this assumption does not hold, we will explore appropriate measures for the data analyses.

#### *5.4 Additional analyses/Compensatory analyses*

A set of additional analyses will be performed to confirm the robustness of main the analyses. We will perform a 1-dimension curve analysis using an Statistical Parametric Mapping 1 package (SPM1D) available for MATLAB (<http://www.spm1d.org>) (33) to study whether acceleration values (i.e., expressed as ENMO [mg]) identify a significant increase in physical activity during the exercise program in comparison with the physical activity pattern at baseline for the control and exercise groups.

In-depth analysis of intervention compliance is going to be conducted to gauge the intensity as exploratory analysis. Changes in others outcomes will be also analyzed using a similar protocol as described by ‘5.2 Analysis methods’ by following the intention to treat and per protocol principles. Furthermore, cross-sectional analyses will be performed using the baseline data of the RCT.

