## 2.4 Framework

A superiority hypothesis testing framework is used, emphasizing the evaluation of a intervention's positive impact compared to a control group. In the main analysis, we compare

resistance exercise group versus control group (no exercise) in 3-time points (Baseline, 12-week and 24-week).

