#### Other outcomes

*Biological samples* (Time frame: Baseline and 24-week). Several biomarkers using blood, saliva, and fecal samples are determined. Blood samples are used to determine traditional blood markers and genotyping and novel blood brain-based biomarkers. In addition, fecal and saliva samples are used to determine microbiome composition and others potential biomarkers.

*Physical Function* (Time frame: Baseline, 12-week and 24-week; gait parameters and 2-km walking test not performed at 12-week). The Senior Fitness Test (SFT) (39) and the Short Physical Performance Battery (SPPB) (40), the 2-km test (only baseline and 24-week) and the Optogait are performed. Briefly, we measure (i) aerobic capacity [i.e., 6-minute walk test (m/6 min) (41), Two-minute step test (n/2 min), Up and Go test (sec) and 2-km walking test (seconds) (42), Chair Sit and Reach Test (cm)], (ii) balance [i.e., Balance test (score of Balance test)], (iii) flexibility [i.e., Chair Sit and Reach test (cm) and the Back Scratch test (cm)] and (iv) gait parameters [i.e., Stride length (cm), Stride time (sec), Step length (cm), Step time (sec)] by the optical Opto Gait system (Microgate Slr; Bolzano, Italy) (43).

*Muscular strength* (Time frame: Baseline, 12-week and 24-week; Gummex Iso-2 dynamometer not performed at 12-week). Measurements are taken to assess both lower and upper muscular strength. Lower body strength was evaluated using the Chair Stand test from SFT (44) and the Gummex Iso-2 dynamometer (EASYTRCH s.r.l., Italy) (45). Upper body strength was assessed through the Arm Curl test from SFT (44), Hand dynamometer (TKK 5101 Grip D, Takey, Tokyo Japan) and the Gummex Iso-2 dynamometer (EASYTRCH s.r.l., Italy) according to the previous published protocol (45).

*Physical activity monitoring* (Time frame: Baseline and 12-week). Movement behaviors are monitored using the Actigraph GT3X + accelerometry device (Pensacola, FL, USA). Participants wear the device on their non-dominant wrist for a continuous span of 9 days, with removal only during activities such as showering. Alongside the device, participants maintained a diary to record in-bed and out-of-bed times, naps, and periods when the device is not in use.

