### 5.2.1 Primary analysis.

#### Effects on primary outcomes

To investigate the overall effect of the resistance exercise intervention on the change from baseline to post-intervention in the executive function composite score, cLMM approach with repeated measures over time (baseline, 12-week and 24-week outcomes) will be used using an intention-to-treat principle. This statistical linear mixed model will include both a random intercept for each participant and a group-by- time interaction as a fixed effect.

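### The accelerometer curve analysis in SAP 5.4 names only baseline as comparator; its inferential contrast should be the between-arm difference in change

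*SAP*

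**What the plan says.** Section 5.4 opens with the statement "A set of additional analyses will be performed to confirm the robustness of main the analyses". The first of these is an SPM1D analysis of acceleration curves, whose question is whether there is a "significant increase in physical activity during the exercise program in comparison with the physical activity pattern at baseline for the control and exercise groups". Section 5.1 (Other outcomes) gives the accelerometer schedule as "Time frame: Baseline and 12-week", so each participant contributes one before-after pair of curves.

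Three other places bear on the point. Section 2.4 sets a superiority framework, "emphasizing the evaluation of a intervention's positive impact compared to a control group". The paragraph on other outcomes in 5.2.2 includes "biological biomarkers, physical function, muscular strength, physical activity" in its list and says that "the same analyses as the primary analysis using an intention-to-treat principle and cLMM analysis will be performed". The primary model in 5.2.1, which is carried over in this way, contains "a group-by- time interaction as a fixed effect".

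**The concern.** The only comparator named for the curve analysis is baseline. The two arms appear as the groups in which that comparison is made, not as the things compared. An analyst who follows the sentence would run a paired test in the exercise arm and another in the control arm.

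Two such tests do not answer whether the programme changed activity relative to control. Anything that moves both arms between the two wear periods enters each within-arm change, and randomisation protects against it only if the arms are contrasted directly. A split result, significant in one arm and not in the other, can arise by chance when the arms changed equally. At stake is what is said about activity during the programme: a before-after increase could be credited to the exercise, or a common decline could mask a real difference.

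**Working it through.** The SAP gives no figure for this analysis, so there is nothing to reproduce. The check has two parts.

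**1. Which contrast each section specifies**

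| Place in SAP | Comparator | Arms contrasted? |
|---|---|---|
| 2.4 | control group | yes |
| 5.2.1, primary model | group-by-time term | yes |
| 5.2.2, other outcomes, including physical activity | same model as 5.2.1 | yes |
| 5.4, SPM1D curves | baseline | not stated |

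**2. How often two within-arm tests mislead (illustration)**

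Inputs from the SAP: two-tailed alpha of 0.05 (3.1); 45 per arm (2.1); dropout of at most 20% (2.3), which leaves 45 × 0.8 = 36 per arm.

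Assumptions not in the SAP: a shift d common to both arms, from 0 to 0.5 SD of the individual change; no programme effect; independent arms; one scalar summary standing in for the curve.

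Probability of a significant increase within one arm: u = 1 − Φ(1.96 − d√n). 
Probability of exercise significant and control not: u(1 − u).

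Example with n = 45 and d = 0.3: √45 = 6.708; 1.96 − 0.3 × 6.708 = −0.052; u = 0.521; u(1 − u) = 0.521 × 0.479 = 0.250.

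| d (SD) | n = 45: u | n = 45: exercise yes, control no | n = 36: u | n = 36: exercise yes, control no |
|---|---|---|---|---|
| 0 | 2.5% | 2.4% | 2.5% | 2.4% |
| 0.1 | 9.9% | 8.9% | 8.7% | 7.9% |
| 0.2 | 26.8% | 19.6% | 22.4% | 17.4% |
| 0.3 | 52.1% | 25.0% | 43.6% | 24.6% |
| 0.4 | 76.5% | 18.0% | 67.0% | 22.1% |
| 0.5 | 91.8% | 7.5% | 85.1% | 12.7% |

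A simulation with t-tests (40,000 replicates; d = 0, 0.2, 0.3 and 0.5) agrees. At 45 per arm the split pattern came out at 2.4%, 19.3%, 24.8% and 8.6%. The two-sample test on change rejected in 4.7% to 5.1% of replicates across both sample sizes, and in favour of exercise in 2.3% to 2.6%, whatever the shift.

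The split pattern is directional, so its proper comparator is the 2.5% in favour of exercise, not the two-sided 5%. The 25% is also the ceiling: u(1 − u) cannot exceed 0.25 and reaches it at u = 0.5, which for n = 45 is d = 1.96/6.708 = 0.29.

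**The case against.** The strongest reply is that the randomised comparison is already planned. Physical activity is among the other outcomes in 5.2.2, analysed with the primary model and its group-by-time term, and the second paragraph of 5.4 again refers changes in other outcomes back to 5.2. This stands. A reader might infer from 5.4 that the plan discards the between-arm comparison of activity altogether; the documents do not support that.

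The sentence is also loose. It names no test, and a group-by-time SPM1D may have been meant. The second half of the 5.4 heading (Compensatory analyses) leaves room for a descriptive question about whether each arm's own pattern shifted, although the SAP does not define the term. Both points are fair. They are reasons to state the contrast, because the wording as it stands leads to within-arm tests.

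A reader might further infer that season or familiarity with the device is known to bias the result. The SAP does not show this. Randomisation is rolling (2.2) and recruitment began in March 2021 (4.1), but no accrual length is given. If entry was spread over the year, seasonal shifts would partly cancel in the arm mean and add variance instead of a common shift. Device effects are not discussed at all. A common shift is therefore possible but assumed.

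Finally, the control arm is tested too. At 45 per arm and 0.5 SD, both arms would show an increase in about 84% of trials (0.918 × 0.918 = 0.843), which would expose the artefact. That safeguard is weak at shifts of about 0.2 to 0.4 SD, where the split is most frequent.

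**Conclusion.** The point holds for the SPM1D analysis in 5.4 and no further. As worded, it amounts to two before-after tests, and a significant result in one arm only would not be evidence of a programme effect. With 45 per arm, no programme effect and an assumed common shift between 0 and 0.5 SD, the misleading split occurs in about 2% to 25% of trials, against 2.5% in favour of exercise for a between-arm test. The range rests on the assumed shift and on a scalar stand-in for the curve; the logic does not depend on either.

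The stakes are small. The sentence that opens 5.4 might suggest that the main result leans on this analysis, but an activity curve can neither confirm nor overturn the executive-function comparison, and no primary conclusion depends on it. This is a worthwhile clarification, not a flaw in the main analysis.

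**What to change.** Add one sentence to 5.4: for each participant compute the change curve (12-week minus baseline ENMO), and compare the arms' change curves with a two-sample SPM1D test as the inferential result. With two time points this is the group-by-time contrast. Report the within-arm curves as description only, without conclusions drawn from one arm being significant and the other not.

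No new data or software are needed. The cost is a wider error band than a paired test gives: with equal arms and equal SD of change, the standard error is SD × √(2/45) = 0.211 SD instead of SD × √(1/45) = 0.149 SD, a factor of √2 ≈ 1.41. That is the price of answering the between-arm question.

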#### *5.5 Harms*

Any situation that may occur, such as injury, emergency or scheduled surgery was reported as adverse events categorize based on predefined criteria using common terminology criteria (i.e., mild, moderate, severe) (6). Sensitivity analyses will be done with all randomly assigned study participants who encountered adverse events that may have impacted the primary outcomes of the analyses.

#### *5.6 Statistical software*

The analyses of the primary outcomes will be performed using R. For the main analyses, we will use the ‘LMMstar’, lmer, nlme and lavaan packages. The use of specific packages will be reported in each manuscript. In addition, specific software’s are used for secondary brain outcomes.

